Low Dose IV Dexamethasone in Prolonging Caudal Anesthesia in Children Undergoing Genitourinary Surgery

**Indiana University School of Medicine
Riley Hospital for Children**

**Principal Investigator: [name]
Co-Investigators: [name]; [name],
MD**

**Version Date:
05/13/2016**

Introduction:

Caudal injection of local anesthetic is a neuraxial technique routinely performed on young children for postoperative analgesia after lower abdominal and lower extremity surgical procedures. One of the major limitations of the use of single shot neuraxial injections for this purpose is the limited duration of action of the injected local anesthetic. Adjuvant medications, such as clonidine and epinephrine, have been added to the local anesthetic to prolong the duration of the neuraxial block, with varying results. Dexamethasone is a synthetic glucocorticoid steroid commonly used in the perioperative setting for a multitude of indications, including the prolongation of local anesthetic based analgesia. The administration of dexamethasone either intravenously or via perineural injection can significantly increase the duration of analgesia derived from a local anesthesia based peripheral nerve block. Literature also suggests that the effect of dexamethasone is equivalent when given intravenously or perineurally. Interest in dexamethasone enhanced caudal analgesia exists, and a previous study noted that caudal anesthesia can be prolonged by intravenous dexamethasone. The study was criticized for using a higher dose of dexamethasone (0.5 mg/kg) than is routinely used in the pediatric population outside of airway procedures, which may expose patients to dose related side effects of dexamethasone. A large meta-analysis has suggested that 0.1 mg/kg is effective for analgesic prolongation, but no direct study of low dose intravenous dexamethasone in combination with caudal anesthesia has been performed.

Rationale/Specific Aim

As dexamethasone is an inexpensive and commonly used medication, it would be beneficial to know if a similar prolongation of analgesia occurs when a local anesthetic is given neurally in combination with low dose intravenous dexamethasone. This project will investigate the efficacy of low dose intravenous (IV) dexamethasone in prolonging the duration of post-operative analgesia provided by an intraoperative caudal injection of local anesthetic.

Inclusion/Exclusion:

Inclusion Criteria:

- Age 2 years-10 year
- Scheduled for elective inpatient genitourinary surgical procedure
- Caudal anesthesia within standard of care for surgical procedure
- Have provided parental consent and assent in accordance with the Institutional Review Board requirements

Exclusion Criteria

- Abnormal/difficult anatomy
- Known allergy to ropivacaine or dexamethasone
- History of documented chronic pain
- Existing infection at site of intended injection

Enrollment:

All patients will be enrolled in the study the day of surgery, in area private hospital setting. Subjects/subject parents may be approached to consent either before or after surgery, provided all inclusion criteria is met and no exclusion criteria. The study will be explained by a member of the research team with extensive knowledge of the protocol. All medications and techniques utilized for this study are commonly accepted for routine care for these patients.

Study Procedures:

1. Study design: prospective data collection.
2. Comparison Groups: We will collect data on 94 subjects having a GU procedure and caudal as standard of care. We will collect information on 47 subjects who receive caudal only. We will collect information on an additional 47 subjects who receive a caudal and IV dexamethasone. No other adjuvant medication will be used.
3. Study and timeline of interventions
 - a. Preoperative: Patients enrolled in this study may receive 0.5mg/kg up to 15mg total of oral midazolam if deemed necessary for anxiolysis by operating room or study anesthesiologist, 15 to 30 minutes prior to anesthetic induction.
 - b. Intraoperative: Subjects will undergo induction of anesthesia by inhalation of sevoflurane and oxygen. An intravenous catheter (IV) will be placed, followed by 2-3mg/kg of propofol if necessary. The airway device (LMA or ETT) will then be placed. Following confirmation of airway placement, the patient will be rolled in left or right lateral decubitus position and caudal epidural will be placed under sterile conditions. To be enrolled as caudal + IV dexamethasone, subjects must receive IV dexamethasone right after caudal placement. Should the IV dexamethasone be given at the end of the surgical procedure, subject will be considered a screen failure. All patients will be maintained on sevoflurane in accordance to patient anesthetic requirements as determined by anesthesia provider.
 - c. Postoperative: All patients will receive routine PACU care. Pain and anxiety scores will be recorded according to routine PACU practice. All patients will have their pain orders written by the anesthesia acute pain service and pain scores monitored per hospital protocol. The patient will have a final pain evaluation by the Acute Pain Service attending the day following caudal placement.
 - d. Measured end-points:
 - i. Type of procedure
 - ii. Time of caudal
 - iii. Length of surgical procedure
 - iv. Time to first analgesic dose
 - v. Amount of pain medicine received in PACU
 - vi. Amount of pain medicine received during floor stay
 - vii. Pain scores over 24 hour period as obtained by floor nurse during routine care

- viii. Patient/parent satisfaction
- ix. Highest pain level in 24 hour period
- x. Adverse events

Risks to patient/ adverse event response:

Per inclusion criteria, patients enrolled in this study will be receiving anesthesia, surgery, and a caudal as standard of care. IV dexamethasone will be given at the discretion of the anesthesiologist. Risks related to the study are limited to potential loss of confidentiality.

Subject Withdrawal:

A patient may withdraw from enrollment at any time. At the time of withdrawing, data already collected will be kept and utilized, but no more data for the study will be collected.

Statistical Considerations:

A two tailed paired t-test will be utilized to evaluate a clinically significant difference of 2 hours between the two groups. Each group will contain 47 participants in order to achieve a power of 0.9 and Alpha of 0.05.

Privacy/Confidentiality:

Participant privacy is an important goal of the researchers. Only the principal investigator and IRB approved study personnel will have access to identifiable data. PHI will be stored in the locked Anesthesiology Offices.

Follow up/Record Retention:

The participation in the study begins with induction of anesthesia and ends after the 24 hour follow up. The patient data related to the study will be passed on to the principal and co-investigators, and the anesthetic record will be placed in the patient's medical chart. Data will be entered and stored securely in a REDCap database. Following completion of the study and after the require amount of time per Indiana Laws, all copies of data collected will be physically destroyed.

References:

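### Operating-room analgesics and caudal concentration and volume are neither standardised nor listed as data, so this clinician-choice comparison cannot show or adjust for group differences in them

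*Combined protocol and SAP*

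**What the plan says.** All references are to the combined protocol and SAP.

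- **Analgesic data (Study Procedures, item 3d).** Two amounts are listed: "Amount of pain medicine received in PACU" and "Amount of pain medicine received during floor stay". Neither covers the operating room.
- **Duration (item 3d).** The entry is "Time to first analgesic dose", with no time zero and no rule for a dose given during surgery.
- **The block (items 3d and 3b).** The only listed variable is "Time of caudal". The procedure text says that the "caudal epidural will be placed under sterile conditions", without drug, concentration or volume. Ropivacaine appears only in the allergy exclusion.
- **Intraoperative care (item 3b).** "All patients will be maintained on sevoflurane in accordance to patient anesthetic requirements as determined by anesthesia provider". Opioids, NSAIDs and acetaminophen are not mentioned, either as permitted or as barred.
- **Adjuvants (item 2, Comparison Groups).** "No other adjuvant medication will be used".
- **Allocation (Risks to patient/ adverse event response).** Whether a child gets IV dexamethasone is left to the anesthesiologist. Item 1 describes the design as prospective data collection. Enrollment allows consent before or after surgery.
- **Source record (Follow up/Record Retention).** Participation starts at induction, and the anesthetic record goes into the medical chart.

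**The concern.** The stated aim is the duration of analgesia provided by the caudal. Two things other than dexamethasone bear directly on when a child first needs an analgesic: what was injected into the caudal space, and which systemic analgesics were given before the child left the operating room. In a randomised trial, chance would tend to balance these. Here nothing in the plan does so.

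The only planned analysis is an unadjusted t-test. If the groups differ in either exposure, the test attributes the resulting difference to dexamethasone, or hides a real effect. Item 3d lists procedure type and surgical length but omits these more direct determinants, so the planned data set could not show whether the groups were comparable on them.

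**Working it through.** **Step 1. The plan's own figure.** Statistical Considerations gives 47 per group, a 2 h difference, power 0.9 and two-tailed alpha 0.05, but no SD. The 47 can therefore only be solved backwards. For two independent groups (normal approximation):

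SD = 2 × √(47/2) / (1.960 + 1.282) ≈ 2.99 h.

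This is circular, not a reproduction. I use an assumed SD of 3.0 h for scale; that gives n = 48 per group and power 0.898 at 47. I treat the groups as independent because they are separate children (the paired test is a separate matter). I also take time to first analgesic dose as the quantity tested, since the plan does not name it.

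**Step 2. Bias from unequal use.** Let an operating-room analgesic delay the first postoperative dose by c hours, and let its use differ between groups by dp. Then

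bias = c × dp.

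With SE = 3.0 × √(2/47) = 0.619 h and no dexamethasone effect, the two-sided rejection rate is Φ(bias/SE − 1.96) + Φ(−bias/SE − 1.96). Neither c nor dp is in the documents; both are assumptions.

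| c (h) | dp | bias (h) | share of 2 h | rejection rate |
|---|---|---|---|---|
| any | 0 | 0 | 0% | 5% |
| 1 | 0.20 | 0.2 | 10% | 6% |
| 2 | 0.20 | 0.4 | 20% | 10% |
| 2 | 0.25 | 0.5 | 25% | 13% |
| 3 | 0.30 | 0.9 | 45% | 31% |
| 4 | 0.25 | 1.0 | 50% | 37% |
| 4 | 0.40 | 1.6 | 80% | 73% |

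The sign can go either way. If the caudal-only group had the greater use, a true 2 h effect would appear as 2 − 1.0 = 1.0 h in the 4 h, 25-point case. The chance of detecting it would then be about 37% instead of 90%.

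**Step 3. Balanced use.** If half of each group receives the drug there is no bias, only extra spread: SD = √(3.0² + c² × 0.25). For c = 2 h this is 3.16 h and power 0.866; for c = 4 h it is 3.61 h and power 0.767.

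**Step 4. Caudal concentration and volume.** The same product applies, with c as the difference in block duration between two make-ups. The documents give no basis for a value, so I put no number on it.

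**Step 5. Does the adjuvant sentence close the gap?** It bars other adjuvants. Against that:

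- It is not among the Exclusion Criteria. Item 3b makes dexamethasone at the end of surgery a screen failure, but nothing equivalent is written for a caudal additive.
- Consent may follow surgery, so a child who has already had an additive would meet every listed criterion.
- No listed field would show compliance.
- On any reading it leaves concentration and volume open.

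**The case against.** **The data may be recoverable.** A reader might infer that these exposures can never be separated from the dexamethasone effect. The documents do not support that. Participation begins at induction and the anesthetic record is kept in the chart, so the items could probably be abstracted. What stands is that they are not planned data and no adjustment is planned.

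**The direction is not settled.** A reader might infer that carry-over is counted as caudal duration. Because time zero and the handling of operating-room doses are undefined, that is only one possibility. If an operating-room dose counts as the first dose, that child's time becomes shorter.

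**The caudal is not wholly open.** The allergy exclusion implies ropivacaine, and the adjuvant sentence bars additives. The Introduction uses the term for additives to the block: "Adjuvant medications, such as clonidine and epinephrine, have been added to the local anesthetic to prolong the duration of the neuraxial block". Yet item 2 places its sentence straight after the IV dexamethasone group, so the word "other" there treats a systemic drug as an adjuvant, and a wider reading is possible. This objection stands: the gap in the block itself is concentration and volume, plus an additive bar with no stated enforcement. Whether systemic analgesics fall under the bar is unclear.

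**The imbalance is assumed.** No passage says who chooses intraoperative analgesics or links that choice to dexamethasone. The range must therefore start at zero.

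**Restricting to children without late intraoperative analgesics is unsafe.** Dexamethasone follows directly after the caudal, so later analgesic use may be a consequence of dexamethasone or of a failing block. Selecting on it could create bias. This objection stands in full.

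**Conclusion.** The concern holds as a gap in planned data and analysis. Operating-room systemic analgesics and caudal concentration and volume are neither standardised nor listed, in a comparison where the clinician chooses the exposure. The data that the plan collects cannot show whether the groups differ on them, nor adjust if they do.

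The size is unknown. It is zero if use is balanced and c × dp hours otherwise. The illustrations run from 0.2 h (10% of the target) to 1.6 h (80%), in either direction, on assumed delays and imbalances and an assumed SD of 3.0 h. They show that a material bias is possible, not that one is present. The change should be made: the unadjusted test, run as written, could credit these exposures to dexamethasone, and the remedy is cheap.

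**What to change.** 1. Add to item 3d, abstracted from the anesthetic record: each intraoperative systemic analgesic (drug, dose, time), and the caudal drug, concentration, volume and any additive.
2. Report these by group.
3. State the time zero for time to first analgesic dose and whether an operating-room dose counts.
4. Add a duration comparison adjusted for the caudal make-up. This is set before dexamethasone is given, so adjusting for it does not condition on a consequence of treatment.
5. Describe by group the intraoperative analgesics given after dexamethasone, or use them in a sensitivity analysis flagged as conditioning on a post-treatment variable. Do not restrict to a subset defined by them.
6. Reconcile the adjuvant sentence in item 2 with the Exclusion Criteria and the screen-failure text in item 3b, and apply any resulting rule before outcomes are seen.

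The cost is a few extra abstracted fields and some lines of text. If reconciliation produces an eligibility rule on additives, some children may become ineligible. Care is unchanged.

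### Dexamethasone is given by clinician choice, but the only planned analysis of its efficacy adjusts for no factor that affects time to first analgesic

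*Combined protocol and SAP*

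**What the plan says.** - **Aim** (Rationale/Specific Aim): "This project will investigate the efficacy of low dose intravenous (IV) dexamethasone in prolonging the duration of post-operative analgesia".
- **Assignment** (Risks to patient/ adverse event response): "IV dexamethasone will be given at the discretion of the anesthesiologist".
- **Groups** (Study Procedures, item 2): "We will collect information on 47 subjects who receive caudal only", and a further 47 who receive a caudal and IV dexamethasone. Item 1 describes the design as prospective data collection and does not claim randomisation.
- **Timing and entry** (Study Procedures, 3b, and Enrollment): to count in the dexamethasone group, "subjects must receive IV dexamethasone right after caudal placement". Also, "Should the IV dexamethasone be given at the end of the surgical procedure, subject will be considered a screen failure", and "Subjects/subject parents may be approached to consent either before or after surgery".
- **Analysis** (Statistical Considerations): "A two tailed paired t-test will be utilized to evaluate a clinically significant difference of 2 hours between the two groups". The only other sentence there gives 47 per group for power 0.9 and alpha 0.05.
- **Data recorded** (Study Procedures, 3d): type of procedure and "Length of surgical procedure" are on the list of measured end-points. Neither has a role in the analysis. Age is not on that list, but it must be known to apply the 2 to 10 year eligibility limit.

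**The concern.** Efficacy is a causal claim. When the clinician decides who gets the drug, the groups may differ in prognosis as well as in treatment, and a plain comparison of means cannot separate the two. The protocol describes no randomisation, matching, stratification or covariate adjustment. Three features make this more than a formality.

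1. Eligibility covers ages 2 to 10 and any elective inpatient genitourinary operation for which a caudal is standard, so age, procedure and duration can vary widely.
2. The caudal is placed before surgery. If time to first analgesic runs from the caudal, the interval contains the operation, and a difference in surgery length shifts the outcome directly.
3. Consent may follow surgery, and late dexamethasone removes a child from the study. Entry can therefore depend on events after the caudal.

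Imbalance could mimic part of the 2-hour difference or hide a real one. A larger sample would not cure either.

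**Working it through.** **Inputs.** From Statistical Considerations: 47 per group, difference 2 h, power 0.90, two-sided alpha 0.05. The documents give no SD, no imbalance and no covariate effect; values for these below are back-solved or assumed.

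**1. The plan's own figure.** Without an SD, 47 cannot be reproduced independently, but the SD it implies can be found. For two independent groups, normal approximation: SD = 2 / [(1.960 + 1.282) × √(2/47)] = 2.99 h. With the noncentral t on 92 df, SD = 2.96 h. So 47 per group fits an unstated SD of about 3 h. The standard error of the difference is then 2.96 × √(2/47) = 0.611 h.

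**2. How imbalance becomes bias.** For a yes/no factor, bias = (shift in time to first analgesic) × (difference between groups in its proportion). Assumed examples:

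- 2 h × 20 points = 0.4 h
- 3 h × 30 points = 0.9 h

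**3. Effect of a bias b.** Noncentral t, 92 df, noncentrality b / 0.611 when the drug has no effect, and (2 − b) / 0.611 when the true effect is 2 h and the bias runs against the drug.

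| Bias (h) | False-positive rate | Power for a true 2 h effect |
|---|---|---|
| 0 | 5.0% | 0.90 |
| 0.2 | 6.2% | 0.83 |
| 0.4 | 9.9% | 0.74 |
| 0.6 | 16.3% | 0.62 |
| 0.9 | 30.8% | 0.43 |

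The false-positive rate reaches 10% at b = 0.402 h. Power falls to 0.80 at b = 0.271 h. The 0.4 h result depends on the SD: 12.0% at 2.5 h and 8.5% at 3.5 h.

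**4. Power of an adjusted analysis at 47 per group.** SE = 2.96 × √(1 − R²outcome) × √(2/47) / √(1 − R²treatment), with 5 covariate degrees of freedom (87 df). R²treatment is the share of treatment choice that the covariates explain; R²outcome is the share of outcome variance.

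| R²treatment | R²outcome | SE (h) | Power at 2 h |
|---|---|---|---|
| 0 | 0.2 | 0.546 | 0.95 |
| 0.1 | 0.1 | 0.611 | 0.90 |
| 0.2 | 0.1 | 0.648 | 0.86 |
| 0.3 | 0.1 | 0.692 | 0.82 |
| 0.3 | 0 | 0.730 | 0.77 |

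The last row is a floor for loss of precision: covariates that explain none of the outcome do not confound it.

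**5. Setting undosed children to 24 h.** For normal times with SD 2.96 h, capping at 24 h lowers a mean m by 2.96 × [φ(d) − d × Q(d)], where d = (24 − m)/2.96, φ is the normal density and Q its upper tail. At m = 20 h this is 0.12 h and at m = 22 h it is 0.44 h, so a true 2 h difference becomes 2 − 0.44 + 0.12 = 1.68 h. For control means of 6 to 14 h it stays at 2.00 h.

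**The case against.** The study is openly observational, and lack of randomisation is not in itself an error. That stands: the defect is the efficacy aim combined with the absence of any plan for confounding.

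A reader might infer that the groups are confounded, or that any difference between them biases the result. The documents support neither. Only differences in factors that affect analgesic duration matter. Discretion may reflect provider habit rather than the child's prognosis, and the protocol does not say which. Eligibility narrows the case mix, while the ban on other adjuvants and pain orders from one service standardise co-treatment. These features limit imbalance but do not correct for it.

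The word paired might suggest matching. No pairs or matching variables are defined, and the groups are separate sets of children. The test name is an inconsistency of its own: arbitrary pairing neither creates nor removes confounding.

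All bias sizes above are assumed. The 0.9 h row needs a 30-point imbalance in a factor worth 3 h, more than the 2 h target, and should not drive the judgement.

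**Conclusion.** The concern holds for the omission. Treatment is chosen by the clinician, the aim is efficacy, and the only planned analysis leaves prognostic imbalance uncorrected, although two relevant covariates are recorded and a third is known. Confidence is high on that, but not on the size of the effect. It would be wrong to conclude that the result will be biased, or by how much, because the documents do not show whether or how far dexamethasone use tracks prognosis. As an illustration resting on the implied SD of 2.96 h, a bias of 0.4 h, one fifth of the target difference, would double the false-positive rate to about 10%.

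**What to change.** Replace the paired t-test with one prespecified primary model: linear regression of time to first analgesic dose on dexamethasone group, adjusted for type of procedure (a few categories fixed in advance), age and length of surgery. Actual length is a proxy for expected length, since dexamethasone is given before the operation's length is known. The model keeps the 2-hour scale.

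- **State the assumptions.** The plan names no primary endpoint, no time origin and no start for the 24-hour window. Measuring from the caudal, and setting children with no analgesic to the end of the 24-hour observation period, are assumptions that the sponsor should confirm or replace. The cap matters only if times run long (step 5 of the check).
- **Withdrawals and undosed children.** Treat children with no first dose, including withdrawals, as censored in a prespecified Cox sensitivity analysis. Report how many withdrawals the linear model leaves out.
- **Secondary.** Report the unadjusted independent-samples comparison.
- **Wording.** Present the result as an adjusted association rather than efficacy. Unmeasured confounding, provider choice and selection through consent after surgery remain, and adjusting for a proxy reduces bias without guaranteeing its removal.

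**Cost.** A little more analysis on data already held, and a more modest conclusion. Restate power at 47 per group as an assumed range of about 0.77 to 0.95; this takes the SD of 2.96 h to hold for the capped times. No extra patients are proposed.

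### The operator is neither a listed study item nor a term in the analysis, so if dexamethasone use follows the anesthesiologist, operator practice is confounded with the drug and the standard error may be too small

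*Combined protocol and SAP*

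**What the plan says.** Study Procedures item 1 reads "Study design: prospective data collection", and item 2 fixes the groups by quota: 47 children with caudal alone and 47 with caudal plus IV dexamethasone. No randomization is described anywhere. The section on risks to the patient says that "IV dexamethasone will be given at the discretion of the anesthesiologist".

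On the block, Study Procedures item 3b says only that "caudal epidural will be placed under sterile conditions". It does not name who places it and gives no local anesthetic volume or concentration. A child counts in the dexamethasone group only if the drug follows the block directly; a child given it at the end of surgery is a screen failure. More than one clinical role appears: item 3a allows premedication "if deemed necessary for anxiolysis by operating room or study anesthesiologist", and item 3b leaves sevoflurane maintenance to the anesthesia provider.

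Item 3d lists ten measured items (i to x). They include procedure type, time of the caudal and length of surgery, but neither the person who chose dexamethasone nor the person who placed the caudal.

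Statistical Considerations gives the whole analysis: a two-tailed paired t-test for a 2-hour difference. It adds: "Each group will contain 47 participants in order to achieve a power of 0.9 and Alpha of 0.05". It defines no pairs and gives no covariate, operator term or standard deviation. Under Follow up/Record Retention, the anesthetic record is filed in the medical chart.

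**The concern.** A clinician's decision, not chance, sets the group. If some anesthesiologists usually give dexamethasone and others usually do not, the two groups will largely come from different clinicians. Any feature of their practice that affects how long the block lasts then enters the group difference. The screen-failure rule may add to this, because clinicians who habitually give the drug late contribute no such children.

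Two things are at stake. The first is bias: the operator effect is added to the drug effect, and adjusting for child or procedure does not remove it. The second is precision: children who share both an operator and a group are not independent, so a test that ignores this can overstate its certainty. The stated aim is efficacy, so the difference will be read as a drug effect. The listed items would not let anyone check whether operator explains part of it.

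**Working it through.** **The plan's own figure.** No standard deviation is given, so 47 per group can be neither confirmed nor refuted. Solving backwards for an unpaired two-sided test: SD = 2 × √(47/2) / (1.960 + 1.282) = 2.99 h by the normal approximation, or 2.96 h with the t distribution. The 2 hours presumably refers to the time until the first analgesic; no primary endpoint is named.

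**Inputs.** From the documents: 94 children, 47 per group, two-sided alpha 0.05, power 0.90, difference 2 h. Assumed, because the documents give none of them: the number of operators K, the within-operator correlation of the outcome (ICC), and how strongly dexamethasone use clusters by operator.

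**Worst case: every operator always or never gives dexamethasone.**

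- Design effect: DE = 1 + (94/K − 1) × ICC
- Real error rate: 2 × [1 − Φ(1.96/√DE)]
- Power with a correct standard error: Φ(3.242/√DE − 1.96), where 3.242 = 1.960 + 1.282

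For K = 10, 94/10 = 9.4 children per operator:

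| ICC | DE | Real error rate | Power |
|---|---|---|---|
| 0.02 | 1 + 8.4 × 0.02 = 1.168 | 0.070 | 0.85 |
| 0.05 | 1 + 8.4 × 0.05 = 1.42 | 0.100 | 0.78 |
| 0.10 | 1 + 8.4 × 0.10 = 1.84 | 0.148 | 0.67 |

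For K = 16 (5.875 children each) and the same ICCs, DE is 1.098, 1.244 and 1.488, and the error rate is 0.061, 0.079 and 0.108.

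**How far this depends on clustered use.** An unpaired t-test was simulated with no true effect and K = 10. Here ρ is the within-operator correlation of dexamethasone use: 0 means unrelated to operator, 1 means always or never.

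| ρ | Error rate, ICC 0.05 | Error rate, ICC 0.10 | True SE / planned SE, ICC 0.10 |
|---|---|---|---|
| 0 | 0.049 | 0.051 | 1.00 |
| 0.3 | 0.060 | 0.089 | 1.15 |
| 0.6 | 0.091 | 0.108 | 1.23 |
| 1 | 0.107 | 0.166 | 1.41 |

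Over K = 6, 10 and 20 and ICC 0.05 to 0.20, the error rate at ρ = 0 stays between 0.045 and 0.057. With operators exactly balanced (9 operators, 5 children per group each), it is 0.048, 0.042 and 0.032 at ICC 0.05, 0.10 and 0.20.

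**Size of a purely operator-driven gap.** With SD 2.96 h, the between-operator SD is 2.96 × √ICC = 0.42, 0.66 and 0.94 h at ICC 0.02, 0.05 and 0.10. Suppose the five operators with the longest blocks always give dexamethasone and the other five never do. For 10 normal values, the means of the upper and lower five differ by 1.48 SD on average. The expected gap is therefore 0.62, 0.98 and 1.38 h.

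**The case against.** The strongest objection is that the mechanism is inferred. The documents do not say that the anesthesiologist who decides on dexamethasone also places the caudal; the text is passive and names several roles. They describe no prescribing habits, and discretion could vary child by child within each operator. In that case the planned standard error is about right, or slightly too wide if operators are balanced. This stands, and it makes the point conditional.

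The list in item 3d is headed as end-points and is not a complete data form; it omits age, for example. Operator identity may be recoverable from the anesthetic record. This also stands: the operator is not a listed study item, which is different from being lost.

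The plan names a paired test, so it does not literally treat all 94 children as independent. But no pairs are defined, and neither a paired test on arbitrary pairs nor an unpaired test takes account of a shared operator.

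Finally, operator is only one route by which unadjusted discretionary allocation can bias the result. That is fair, and it limits the priority of this point. It does not remove it, because adjusting for child and procedure would leave operator differences in place.

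**Conclusion.** The point holds in conditional form. The plan neither lists the operator nor allows for the operator in the analysis, although a clinician's choice sets the group. Confounding by operator, and a standard error that is too small, both need dexamethasone use to cluster by anesthesiologist and block duration to differ between them. With 10 operators in the always-or-never extreme and an ICC of 0.02 to 0.10, the real error rate is about 7% to 15%. With use unrelated to operator it is about 5%, and with balanced operators slightly less. The number of operators, the ICC and the prescribing pattern are all assumptions.

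A reader might infer that the planned intervals are certainly too narrow, or that a few skilled operators could produce the 2-hour difference by themselves. The documents support neither. The first depends on a prescribing pattern they do not describe. For the second, even perfect sorting of 10 operators gives an expected gap of 0.6 to 1.4 h at these ICCs, using an SD that is itself back-solved.

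This is a worthwhile, inexpensive improvement; it does not show that the result would be wrong.

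**What to change.** - **Data.** Add two coded identifiers to the measured items, taken from the anesthetic record: the anesthesiologist who chose whether to give dexamethasone, and the person who placed the caudal. State in advance which of them defines operator in the model.
- **Description.** Tabulate dexamethasone use by operator, with the number of operators who contributed children to both groups.
- **Analysis.** Replace the paired t-test with an independent-groups comparison that includes an operator term (fixed or random intercept), or uses operator-clustered standard errors with a small-cluster correction. Clustered errors repair the precision only. A fixed intercept removes between-operator differences, but draws only on operators present in both groups.
- **Reporting.** Give the within-operator difference among operators who contributed to both groups. If few or none did, state that operator and dexamethasone effects cannot be separated; no model can recover the distinction.

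The cost is two coded fields, one table and a slightly different model. The confidence interval will usually be somewhat wider. Confounding by child or procedure remains and needs its own adjustment.
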